6.8.3.2 Body Weight at Week 24 (Absolute and Percent Change)

Body weight and change from Baseline in body weight at each visit will be summarized by treatment group using standard descriptive statistics. The treatment effects at Week 24 will be evaluated using MMRM statistics with absolute change from Baseline as the endpoint and Baseline body weight-by-time interaction as a covariate. Inferential statistics will be based on the absolute change from Baseline in body weight.

Similarly, percent change from Baseline in body weight will be analyzed using MMRM statistics with percent change from Baseline as the endpoint and with no covariate.

6.8.3.3 Change from Baseline in SBP at Week 16 in the Subset of Patients with Baseline SBP \geq 130 mm Hg

SBP and change from Baseline in SBP at each visit will be summarized by treatment group using standard descriptive statistics. Change from Baseline in SBP at Week 16 in the subset of patients with Baseline SBP \geq 130 mm Hg will be analyzed using MMRM statistics with change from Baseline as the endpoint and Baseline SBP -by-time interaction as a covariate. Descriptive statistics and tests for group differences will be provided for Week 16 and other visits as well.

6.8.3.4 Change from Baseline in Bolus Insulin Dose at Week 24 (as An Average Over The 3-5 Days Prior to The Visit)

For each day with complete insulin data, the daily bolus (for all patients, for patients on pre-mixed insulin, the bolus is defined as the rapid acting component; eg, a patient receiving a daily total of 50 IU of Novolin[®] 70/30 insulin, 15 units (0.3 x 50) is assessed as the "daily bolus" insulin), daily basal (for

Statistical Analysis Plan

Version: Final 1.0

Lexicon Pharmaceuticals Protocol No. LX 4211.1-312-T1DM

Date of Issue: 17 MAR 2017

Covance Study ID: 000000145143

patients using insulin pumps and patients using subcutaneous injections), daily non-bolus (for patients receiving intermediate insulin; eg, a patient taking a daily total of 50 IU of Novolin[®] 70/30 insulin, 35 units (0.7 x 50) is assessed as the “daily non-bolus” insulin) and total daily insulin (for all patients) will be calculated. These calculated values will be entered in the eCRF.

Mean daily bolus insulin dose will be defined as the average of daily bolus insulin doses as calculated above based on results of at least 3 days of data during the preceding 3-5 days (consecutive or nonconsecutive) prior to the clinic visit. Dose on Day 1 will be excluded from Baseline calculation. Mean daily bolus insulin dose and percent change from Baseline in mean daily bolus insulin dose at Week 24 will be summarized by treatment group using standard descriptive statistics. The treatment effects at Week 24 will be evaluated using MMRM statistics with percent change from Baseline as the endpoint and with no interaction covariate. Inferential statistics will be based on the percent change from Baseline in mean daily bolus insulin dose.

In addition, absolute change from Baseline in mean daily bolus insulin dose will be summarized using standard descriptive statistics and the treatment effect will be evaluated using MMRM statistics with change from Baseline as the endpoint and Baseline mean daily bolus insulin dose-by-time interaction as a covariate.

6.8.4 Other Efficacy Analysis

Analysis of other efficacy endpoints will be based on the mITT population, with the exception of the 2 endpoints based on the PSDD-NRS, which will be based on the Satiety substudy population. Descriptive statistics for these efficacy endpoints will be presented by treatment group and by study visit where appropriate. All post-Baseline data will be used in the analyses, including observations occurring after discontinuation of study drug.

For continuous efficacy endpoints, MMRM or ANCOVA model will be used as specified in [Section 6.8](#). The choice in statistical models depends on whether the measurement process is over multiple timepoints (MMRM) or at a single timepoint (ANCOVA).

For binary efficacy endpoints, CMH test and 95% CLs based on normal approximation methods with a continuity correction factor will be used, as described in [Section 6.8](#).

Figures displaying mean change from Baseline by visit, LS mean change, and bar charts displaying proportions, will be presented by treatment groups for selected parameters, as appropriate.

6.8.4.1 Change from Baseline in A1C, Body Weight, SBP, and Bolus Insulin Dose

Change from Baseline in A1C, body weight (absolute and percent change), SBP and mean daily bolus insulin dose (percent and absolute change) are analyzed as secondary endpoints at Week 24. The same MMRM analysis performed for the Week 24 endpoint will be used to extract the results for each visit. Descriptive statistics and tests for group differences will be presented for all visits.

In addition, the frequency and percent of patients achieving an A1C <7.0 will be presented by treatment group and visit.

Summary statistics of mean daily bolus insulin dose as percent of the Baseline measure will also be provided.

6.8.4.2 Proportion of Patients by Visit Achieving an A1C Decrease from Baseline by Various Criteria

The following A1C decrease categories will be assessed by visit:

- $\geq 0.5\%$ absolute in the subset of patients with Baseline A1C $\leq 9.0\%$
- $\geq 1\%$ absolute in the subset of patients with Baseline A1C $\leq 9.0\%$
- $\geq 0.5\%$ absolute in the subset of patients with Baseline A1C $> 9.0\%$
- $\geq 1\%$ absolute in the subset of patients with Baseline A1C $> 9.0\%$
- $\geq 0.5\%$ absolute or $> 10\%$ in the subset of patients with Baseline A1C $\leq 9.0\%$
- $\geq 1\%$ absolute or $> 10\%$ in the subset of patients with Baseline A1C $\leq 9.0\%$
- $\geq 0.5\%$ absolute or $> 10\%$ in the subset of patients with Baseline A1C $> 9.0\%$
- $\geq 1\%$ absolute or $> 10\%$ in the subset of patients with Baseline A1C $> 9.0\%$

The frequency and percent of patients belonging to each A1C decrease category above will be presented by Baseline A1C categories, treatment group and visit and analyzed using the methods described for binary efficacy endpoints in [Section 6.8](#).

6.8.4.3 Proportion of Patients by Visit with Reduction in Body Weight by Prespecified Amounts of $\geq 2\%$, $\geq 5\%$, and $\geq 10\%$

The frequency and percent of patients with reductions in body weight will be presented for the prespecified amounts of: $\geq 2\%$, $\geq 5\%$, and $\geq 10\%$, by treatment group and visit and analyzed using the methods described for binary efficacy endpoints in [Section 6.8](#).

6.8.4.4 Proportion of Patients by Visit Achieving an A1C Reduction $\geq 0.4\%$ and No Increase in Body Weight

The frequency and percentage of patients achieving an A1C reduction $\geq 0.4\%$ and no increase in body weight will be presented by treatment group and visit and analyzed using the methods described for binary efficacy endpoints in [Section 6.8](#).

6.8.4.5 Proportion of Patients Achieving an A1C Reduction $\geq 0.5\%$ at Week 24 and No Episode of SH

The frequency and percentage of patients achieving an A1C reduction $\geq 0.5\%$ at Week 24 without SH events from randomization to Week 24 will be presented by treatment group and analyzed using the methods described for binary efficacy endpoints in [Section 6.8](#).

6.8.4.6 Proportion of Patients by Visit Meeting Success Criteria for A1C and Insulin

The frequency and percentage of patients with decrease from Baseline in mean daily bolus insulin dose of $> 20\%$ and a decrease from Baseline in A1C of $> 0.3\%$ will be presented by treatment group and visit and analyzed using the methods described for binary efficacy endpoints in [Section 6.8](#).

6.8.4.7 Change from Baseline in FPG

Descriptive statistics of FPG (mg/dL) will be presented by treatment group and visit. Change from Baseline in FPG at Week 24 and other visits will be analyzed using MMRM statistics with change from Baseline as the endpoint and Baseline FPG-by-time interaction as a covariate. Treatment effects at Week 24 and other visits will be presented.

6.8.4.8 Change from Baseline in Total and Basal (or Non-bolus) Insulin Dose

Change from Baseline in the following endpoints will be analyzed by visit:

- Mean total daily insulin dose by visit (as an average over the 3-5 days prior to the visit)
- Mean daily basal (or non-bolus) insulin dose by visit (as an average over the 3-5 days prior to the visit)

Change from Baseline in the above endpoints will be analyzed using MMRM statistics with change from Baseline as the endpoint and Baseline dependent variable-by-time interaction as a covariate. Descriptive statistics and tests for group differences will be summarized for all visits.

In addition, percent change from Baseline in mean total daily insulin dose and mean daily basal (or non-bolus) insulin dose will be summarized using standard descriptive statistics and the treatment effect will be evaluated using MMRM statistics with percent change from Baseline as the endpoint and with no covariate.

Summary statistics of mean total daily insulin dose and mean daily basal (or non-bolus) insulin dose as percent of the Baseline measure will also be provided.

6.8.4.9 Change from Baseline in DBP

Change from Baseline in DBP will be analyzed using MMRM statistics with change from Baseline as the endpoint and Baseline DBP -by-time interaction as a covariate. Descriptive statistics and tests for group differences will be summarized by visit.

6.8.4.10 Proportion of Patients by Visit with SBP <140 mm Hg and DBP <90 mm Hg in the Subset of Patients with Baseline SBP ≥140 mm Hg or DBP ≥90 mm Hg

The frequency and percent of patients with SBP <140 mm Hg and DBP <90 mm Hg will be presented in the subset of patients with Baseline SBP ≥140 mm Hg or DBP ≥90 mm Hg, by treatment group and visit and analyzed using the methods described for binary efficacy endpoints in [Section 6.8](#), except the CMH and NRI will be applied to Week 16 instead of Week 24.

6.8.4.11 Proportion of Patients by Visit with SBP <130 mm Hg and DBP <80 mm Hg in the Subset of Patients with Baseline SBP ≥130 mm Hg or DBP ≥80 mm Hg

The frequency and percent of patients with SBP <130 mm Hg and DBP <80 mm Hg will be presented in the subset of patients with Baseline SBP ≥130 mm Hg or DBP ≥80 mm Hg, by treatment group and visit and analyzed using the methods described for binary efficacy endpoints in [Section 6.8](#), except the CMH and NRI will be applied to Week 16 instead of Week 24.

6.8.4.12 Change from Baseline by Visit in Hypoglycemic Events Calculated as a Daily Average over the Week Prior to the Visit

Change from Baseline in the following endpoints will be analyzed by visit:

- Hypoglycemic events/patient/day (≤ 70 mg/dL) by SMBG
- Hypoglycemic events/patient/day (≤ 55 mg/dL) by SMBG

Change from Baseline in hypoglycemic events, calculated as a daily average over the week prior to the visit, will be analyzed using MMRM statistics with change from Baseline as the endpoint and Baseline-

Statistical Analysis Plan

Version: Final 1.0

Lexicon Pharmaceuticals Protocol No. LX 4211.1-312-T1DM

Date of Issue: 17 MAR 2017

Covance Study ID: 000000145143

dependent variable-by-time interaction as a covariate for each of the 2 hypoglycemic event definitions: ≤ 70 mg/dL by SMBG, and ≤ 55 mg/dL by SMBG. Descriptive statistics and tests for group differences will be summarized for all visits.

6.8.4.13 Measures of Kidney Function

Change from Baseline in the following measures of kidney function will be analyzed by visit:

- Urine ACR, CCR, and GCR
- Serum creatinine
- MDRD eGFR

The following equation will be used to derive the MDRD eGFR:

$$\text{GFR (mL/min/1.73 m}^2\text{)} = 175 \times (\text{Scr})^{-1.154} \times (\text{age})^{-0.203} \times (0.742 \text{ if female}) \times (1.212 \text{ if African American})$$

where Scr is serum creatinine reported in mg/dL.

Change from Baseline in serum creatinine and eGFR will be analyzed using MMRM statistics with change from Baseline as the endpoint and Baseline dependent variable-by-time interaction as a covariate. Descriptive statistics and tests for group differences will be summarized for all visits.

Change from Baseline in urine ACR, CCR, and GCR will be analyzed using an ANCOVA model with Baseline dependent variable as a covariate. Descriptive statistics and tests for group differences will be summarized.

6.8.4.14 Proportion of Patients with Satiety Increase $\geq 30\%$ as Measured by The PSDD-NRS (Substudy)

In the Satiety substudy, patients are instructed to complete the satiety daily diary each day before the first meal of the day during the 2-week single-blind placebo Run-in Period (14 days, ± 3 days) and for the last 14 days, ± 3 days of the Double-blind Treatment Period (ie, each day during Weeks 23 and 24). Patient satiety (ie, average level of hunger) is evaluated using an 11-point PSDD-NRS, from 0='very full' to 10='very hungry'.

The 14 days closest to, but not greater than Day 1 (and before start of study drug) will be selected for the Baseline assessment for a patient. The 14 days closest to, but not greater than the Week 24 visit (or the day of the last dose of study drug, if earlier than the Week 24 visit) will be selected for the Week 24 assessment for a patient. For each assessment period, the average of the non-missing PSDD-NRS scores during that period and which were entered in the daily diary before the first meal of the day will be calculated and used in the analysis, provided that the patient has at least 8 such non-missing scores in that period. If the patient has less than 8 non-missing scores for a period which were entered in the daily diary before the first meal of the day, then the patient's PSDD-NRS score is set to missing for that period.

The frequency and percentage of patients with satiety increase $\geq 30\%$ from Baseline at Week 24 will be presented by treatment group for the Satiety substudy population visit and analyzed using the methods described for binary efficacy endpoints at Week 24 in [Section 6.8](#).

Statistical Analysis Plan

Version: Final 1.0

Lexicon Pharmaceuticals Protocol No. LX 4211.1-312-T1DM

Date of Issue: 17 MAR 2017

Covance Study ID: 000000145143

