5.1.3 Unscheduled Visits

During the course of the study, additional contact by telephone call, or unscheduled site visit, (or both) may be considered, based on Investigator's discretion. Assessments completed during these visits (on-site or by telephone call), may include evaluation of SMBG data, insulin doses, AEs (eg, volume depletion, elevated creatinine), hypoglycemic events, etc. The Unscheduled Visit electronic case report form (eCRF) will be completed for each unscheduled telephone contact or site visit.

5.1.4 24-Week Double-blind Treatment Period

Following completion of the single-blind placebo Run-in Period, eligible patients will enter the 24-week, double-blind Treatment Period. Patients will be randomly assigned 1:1 in parallel between the 2 treatment groups: sotagliflozin 400 mg or placebo.

The double-blind Treatment Period includes 5 clinic visits (Baseline, and Weeks 4, 8, 16, and 24).

For all patients, clinic visits should be scheduled in the morning at approximately the same time of day.

In regard to patients taking antihypertensive medications, the Investigator will be asked to maintain dosages unchanged between Baseline and Week 16, if this is consistent with proper medical management of the patient.

For patients in the satiety substudy, the satiety daily diaries completed during the single-blind placebo Run-in Period will be collected at Day 1 (Baseline). At the visit scheduled for Week 16, these patients will receive packets of satiety daily diaries. At the beginning of Week 23, patients will receive a telephone call to remind them to start recording information onto the satiety daily diaries. The patients will be instructed to complete the paper diary each day, before the first meal of the day for the last 2 weeks of the double-blind Treatment Period (ie, during Week 23 and during Week 24, a total of 14 days, ± 3 days). The diaries will be returned to the site at the visit scheduled for the end of Week 24.

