6.3.3 Termination of Study Participation and/or Withdrawal of Consent

A patient has the right to discontinue study participation at any time, for any reason, and may leave the study without specifying a reason. The Investigator should make all efforts to obtain information about possible underlying AEs leading to the decision to withdraw from study participation. Any AE, EOSI, and SAE information elicited must be documented in the patient's source documents and the eCRF.

Unless a patient who prematurely discontinues trial participation specifically withdraws consent for any follow-up contact, all patients will continue to be contacted as specified in the protocol through the end of the study. There are a number of options for continuing follow-up once a patient decides to cease taking study drug. Investigators and site staff should encourage patients to allow as much follow-up as possible, and will need to clearly identify which aspects of the clinical trial the participants are discontinuing. Whenever possible, documentation should be collected in writing as to which of the following options the patient has chosen.

- The patient opts to permanently cease taking study drug only. In this case, the patient continues to complete all study activities per protocol.
- The patient is not willing to continue planned clinic visits/assessments, but will agree to phone call assessments in accord with the clinic visit schedule.
- The patient is not willing to continue planned clinic visits/assessments or phone call assessments, but will allow the Investigator access to their medical records and end-of-study telephone contact.
- The patient is not willing to be contacted but does allow the Investigator access to their medical records/contact with their care provider. In this case, the patient agrees

to continue as a study participant by allowing information collected from his/her medical records to be used for research purposes. The patient does not agree to be contacted via phone, email, and/or postal mail for follow-up visits and/or study updates.

- The patient is not willing to allow any direct contact, access to medical records, or contact with care provider. In this case, public records may be used to confirm vital status at end of study.

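### The last-dose cut-off on the Week 24 satiety score discards scheduled diaries from patients who stop drug early, contradicting the SAP's own rule to use data after discontinuation

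*SAP*

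**What the plan says.** SAP 6.8.4.14 builds the Week 24 satiety score from the 14 days up to the Week 24 visit, "or the day of the last dose of study drug, if earlier than the Week 24 visit". The mean diary score is used "provided that the patient has at least 8 such non-missing scores in that period"; otherwise the score is set to missing. The derivation feeds both satiety endpoints: the responder proportion (6.8.4.14) and the ANCOVA of change from baseline (6.8.4.15).

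The parent section, SAP 6.8.4, sets the data rule: "All post-Baseline data will be used in the analyses, including observations occurring after discontinuation of study drug". It does single out satiety, but only for the analysis population: "with the exception of the 2 endpoints based on the PSDD-NRS, which will be based on the Satiety substudy population". Table 5.1-1 gives the satiety scale a Week 24 window from Day 2 onward, with target Day 169 and no last-dose limit. SAP Section 7, which lists departures from the protocol, does not mention the cut-off.

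Protocol 5.1.4 has the post-baseline diaries handed out at Week 16 and completed "for the last 2 weeks of the double-blind Treatment Period". It adds: "At the beginning of Week 23, patients will receive a telephone call to remind them to start recording information onto the satiety daily diaries". For a patient who stops study drug only, Protocol 6.3.3 states: "In this case, the patient continues to complete all study activities per protocol".

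**The concern.** The cut-off moves the window back in time, but no diaries are scheduled at the earlier time. For an early stopper the rule therefore cannot produce an on-treatment satiety score. It can only turn a collected Week 24 score into a missing one.

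Two things are at stake. First, SAP 6.8.4 and 6.8.4.14 give different instructions, so two programmers could each follow the SAP and obtain different results. Second, the satiety population is a subset of mITT, yet the ANCOVA would be restricted to patients who stayed on drug nearly to the end. Membership of that set is decided after randomization and can differ between arms in number and in kind.

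**Working it through.** **Plan's own figure.** Protocol 10.1 and SAP 2.3 recruit 280 substudy patients to obtain 224 with 20% dropout: 224 / (1 − 0.20) = 280, which reproduces. That is 140 recruited and 112 evaluable per arm. This figure serves here only to size the affected group.

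**Diary days.** Week 23 starts on Day 22 × 7 + 1 = 155 and Week 24 ends on Day 24 × 7 = 168. For last dose on Day L, the number of diaries counted out of 14 is max(0, min(L, 168) − 154):

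| Last dose (Day) | Diaries counted | Week 24 score |
|---|---|---|
| 154 or earlier | 0 | missing |
| 157 | 3 | missing |
| 161 | 7 | missing |
| 162 | 8 | scored, 6 diaries dropped |
| 165 | 11 | scored, 3 diaries dropped |
| 168 | 14 | no loss |

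The threshold is about Day 162; the ±3-day visit and diary windows blur it. A patient who stays on drug loses nothing material: under Protocol 7.3 the morning dose is withheld on visit days, so the last dose normally falls on the day before the visit.

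**What happens to a missing score.** SAP 5.2.1 makes it a non-response at Week 24. For the ANCOVA, SAP 5.2.2 imputes nothing for continuous endpoints, so the patient is left out.

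**How many.** 0.20 × 140 = 28 per arm, or 280 − 224 = 56 in total. This is a ceiling. It requires that all 20% stop before about Day 162, stay in full follow-up and return at least 8 valid diaries. Patients must also have at least 8 run-in diaries to enter the satiety population, so the true denominator is at most 140.

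**Effect on the ANCOVA.** Let d be the on-drug effect. Take the planning assumption in Protocol 10.1, made for the main study, that sotagliflozin patients off drug respond like placebo. Assume also that stopping is unrelated to satiety.
- With the cut-off: about d, from 224 patients.
- With all data: (1 − 0.20) × d = 0.8d, from up to 280 patients.
- Standard error ratio by numbers alone: √(280/224) = 1.118.
- Signal on a common scale: d/1.118 = 0.89d with the cut-off, against 0.80d without it.

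**Effect on the responder difference.** Let pT and pP be on-drug response rates and qT and qP the stopping rates, under the same off-drug assumption.
- With the cut-off: (1 − qT)pT − (1 − qP)pP.
- With all data: (1 − qT)pT + qT·pP − pP.

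If qT = qP = q, both equal (1 − q)(pT − pP). The documents give no response rates. The table assumes pT − pP = 0.20 and varies pP:

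| pT / pP | Stopping qT / qP | Cut-off | All data |
|---|---|---|---|
| 0.40 / 0.20 | 20% / 20% | 0.16 | 0.16 |
| 0.40 / 0.20 | 25% / 15% | 0.13 | 0.15 |
| 0.40 / 0.20 | 15% / 25% | 0.19 | 0.17 |
| 0.30 / 0.10 | 25% / 15% | 0.14 | 0.15 |
| 0.50 / 0.30 | 25% / 15% | 0.12 | 0.15 |

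In these cases unequal stopping moves the difference by 0.01 to 0.03, in either direction.

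**The case against.** A specific derivation normally overrides a general statement, and 6.8.4.14 is detailed enough to look deliberate. It already narrows the wide window of Table 5.1-1. The SAP also uses a last-dose limit elsewhere: Section 6.9.2 stops counting hypoglycemic events at the last dose, which bears on the severe-hypoglycemia component of 6.8.4.5. The Protocol synopsis describes the 224 as completing while still on treatment, so an on-treatment analysis set matches the planned size. And if off-drug patients respond like placebo, including them dilutes the effect by more than the extra patients repay.

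Much of this stands. Two stronger readings that a reader might infer are not supported:
- Satiety is not the only endpoint in 6.8.4 touched by a last-dose limit, as 6.8.4.5 shows.
- The 1.118 ratio is not a shortfall against plan, because 280 evaluable patients were never planned.

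What does not stand is the claim that the conflict is thereby resolved. SAP 6.8.4 names the satiety endpoints and exempts them on population alone, and nothing says that the later clause overrides it. The hypoglycemia cut-off is set out openly in the event rules and, for the primary endpoint, is backed by sensitivity analyses in SAP 6.8.2. The satiety cut-off has no such support. Agreement with the planned 224 does not remove the selection in the ANCOVA.

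**Conclusion.** The inconsistency is real and should be corrected. A patient who stops before about Day 162 and still completes the scheduled diaries is treated as missing, counted as a non-responder and left out of the ANCOVA, against the data rule of the parent section. The size is at most about 28 of 140 per arm and likely smaller, since the documents say nothing on when patients stop or how many of them return diaries.

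The issue is consistency of the estimand and selection bias. A reader might infer that the correction buys power. Under the protocol's placebo-like assumption it does not: the ANCOVA effect moves from about d to 0.8d. A reader might also infer that up to 20% of responder outcomes become false failures. Only off-drug patients who would have responded change status: at an assumed rate of 0.20 that is 0.20 × 0.20 = 4% of an arm, about 6 of 140. With equal stopping and the same assumption, the responder difference does not change at all. Satiety is an other efficacy endpoint outside the testing sequence in SAP 6.8, so primary and secondary conclusions are unaffected.

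**What to change.** In SAP 6.8.4.14, delete the last-dose parenthesis. The main satiety analyses would then use the 14 days up to the Week 24 visit, or up to target Day 169 if there is no visit, regardless of drug status. Keep the requirement of 8 scores. Report the last-dose version as a supplementary analysis labelled on-treatment.

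If the team does intend an on-treatment main analysis, the minimum is to declare it as an exception in SAP 6.8.4 and Section 7 and to report the all-data version beside it.

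The cost is one phrase, a fallback date and one supplementary table, with no new data collection. The downside is possible dilution of the estimated effect, as already accepted for the other endpoints that use post-discontinuation data. The choice should be made before unblinding.
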